## 9. Outcome Measures

### Primary outcome measures

The primary outcome measure is the presence or absence of a paramagnetic rim around chronic active white matter MS lesions, assessed at the end of the dosing period.

Definition of efficacy endpoint: disappearance of one or all paramagnetic phase rims. At each study visit, paramagnetic phase rims will be assessed. For the purposes of dose escalation, if at any on-treatment scan, all paramagnetic rims that were present at baseline are no longer seen, dose escalation will end and the subject will proceed into the post-treatment follow-up phase of the study.

## Secondary outcome measures

- Safety and tolerability: AE tables
- Clinical
  - Expanded Disability Status Scale (EDSS)
  - 9-hole peg test (9HPT)
  - Symbol digit modalities test (SDMT)
- MRI:
  - Proportion of paramagnetic rim lesions in which the rim has diminished or disappeared at any time point
  - Changes in T1 relaxation time within paramagnetic rim lesions at all time points, relative to non-rim lesions
  - Changes in size of paramagnetic rim lesions at all time points, relative to non-rim lesions

## Exploratory outcome measures

Exploratory outcome measures will be derived from clinical scales (may include those mentioned as secondary outcome measures and others, e.g. 25-foot timed walk, paced auditory serial addition test, and Scripps Neurological Rating Scale), MRI parameters ((characteristics/persistence of paramagnetic rims at all time points (qualitative)), and stored biofluids, with focus on immune cell populations (e.g. macrophages, lymphocytes, and subtypes thereof), cytokines (e.g., IL-1 $\beta$ , IL-1Ra, IL-6), and also on protein and other biomarkers of neurodegeneration (e.g. neurofilament light chain). Additional assays (e.g. for anti-anakinra antibodies) may also be performed. These analyses will be performed in NIH labs or through collaboration, either intramural or extramural.

## 10. Statistical Analysis

### Analysis of data/study outcomes

The primary outcome is the per-patient proportion of lesions in which the paramagnetic rim has been modulated at the end of the dosing period. Proportion of diminished/resolved paramagnetic rims will be analyzed by investigators blinded to time point, reported descriptively, and compared to the assumption of no change off therapy (11, 16) — a reasonable assumption since we have never observed complete disappearance of a chronic rim — via Binomial exact tests.

For the secondary outcome measures, safety and tolerability will be assessed qualitatively; AEs will be tabulated and compared to prior published and unpublished (to the extent possible) data on anakinra. Quantification will include the proportion of participants who start anakinra therapy and complete the full dosing. MRI outcomes will be reduced to scalar measures at various time points. Longitudinal changes in rim presence/absence, T1 relaxation time, and lesion volume will be analyzed by analysis of variance or mixed-effects models (which naturally handle missing data), the latter two in comparison to

CNS IRB Protocol Template (5.4.17)

non-rim lesions. Analyses will be performed both in completers and on an intent-to-treat basis. There will be no interim analysis.

Analysis methods for exploratory outcome measures will be determined by the study team and collaborators at a later time point.

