## Précis:

- *Objective.* The overall goal of this study is to determine the safety, tolerability, and radiological efficacy of up to 12 weeks of subcutaneous injection of anakinra in people with multiple sclerosis and evidence, by magnetic resonance imaging (MRI), of chronic active (also known as “smoldering”) lesions in the white matter.
- *Study population.* 5 people with progressive or stable MS, at least one paramagnetic rim lesion on 7-tesla MRI, and no new white matter lesion formation for at least 3 months or clinical relapse for at least 12 months, will complete the study.
- *Design.* In this open label, dose escalation study, participants will receive up to 12 weeks of subcutaneous anakinra with initial dose of 100 mg daily up to a target dose of 300 mg daily. Study visits will occur every 4 weeks while on treatment, with 2 follow-up visits at 4 and 12 weeks after treatment discontinuation.
- *Outcome measures.* The primary outcome measure is disappearance of one or more paramagnetic rims from white matter lesions identified at baseline. Secondary outcomes include safety and tolerability, clinical and radiological outcomes. Exploratory serological and CSF measures will also be obtained to investigate mechanism of action of anakinra and for biomarker development.

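### The primary event is rim disappearance in the Précis and Section 9 but any modulated rim in Section 10; if rims only fade, that difference decides the one-event test

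*Combined protocol and SAP*

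**What the plan says.** The Précis states: "The primary outcome measure is disappearance of one or more paramagnetic rims from white matter lesions identified at baseline". Section 9, Primary outcome measures, states: "The primary outcome measure is the presence or absence of a paramagnetic rim around chronic active white matter MS lesions", and places the assessment at the end of dosing. Both describe a rim that is there or gone.

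Section 10, Analysis of data/study outcomes, differs: "The primary outcome is the per-patient proportion of lesions in which the paramagnetic rim has been modulated at the end of the dosing period". The next sentence brings in fading: "Proportion of diminished/resolved paramagnetic rims will be analyzed by investigators blinded to time point". Exact binomial tests against no change off therapy follow, with the support "a reasonable assumption since we have never observed complete disappearance of a chronic rim".

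Section 10, Power analysis, holds the only rejection rule. It takes a null proportion of 0.01 of individuals with lesion changes, 5 participants, a one-sided exact binomial test at 0.05 and 80% power for a difference of 0.27. It rejects on one individual with at least one lesion change. The null is drawn from 1 of 29 individuals with subtle changes over several years.

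Two further provisions matter:
- **Stopping and replacement.** Section 4, Study overview, allows the drug to be stopped early once the efficacy endpoint is reached. Section 9 moves a participant to follow-up when "all paramagnetic rims that were present at baseline are no longer seen". The Power analysis replaces dropouts and anyone taken off anakinra, until there are 5 completers or the accrual ceiling is reached.
- **Analysis sets.** Section 10 plans both completer and intent-to-treat analyses and does not rank them.

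**The concern.** A rim that fades but stays visible is a primary event in Section 10 and not one in the Précis or Section 9. *Modulated*, *diminished* and *lesion change* are not defined. The unit moves as well. Section 10 first names a proportion of lesions within each patient, which is not a yes/no outcome, and then applies a rule that counts individuals.

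One participant settles the test, so the definition of the event carries unusual weight. If it is left open, it can be chosen after the scans have been read. The same holds for the analysis set when a participant is stopped because the rims resolved.

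**Working it through.** **Inputs** (Section 10, Power analysis): n = 5; null rate 0.01; alternative 0.01 + 0.27 = 0.28; one-sided exact binomial at 0.05; reject on 1 event; natural history 1/29.

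**1. The plan's own figure.** Type I error = 1 − 0.99^5 = 0.0490. Power = 1 − 0.72^5 = 0.8065. The stated 80% power at 0.05 is reproduced.

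**2. The two definitions under the one-event rule.** Disappearance is taken as one or more rims, as in the Précis. In rows 2 and 3 one participant is affected.

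| State at end of dosing | Précis / Section 9 | Section 10 |
|---|---|---|
| No rim changed | 0/5, p = 1 | 0/5, p = 1 |
| A rim faded, none gone | 0/5, p = 1 | 1/5, p = 0.049 |
| A rim gone | 1/5, p = 0.049 | 1/5, p = 0.049 |

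Only the middle row differs, and there the conclusion reverses.

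**3. Is 0.01 tenable if fading counts?** Assume that several years means 2 to 5 and that the hazard is constant. The 12-week rate is 1 − (28/29)^((12/52)/years), which is 0.0040 for 2 years and 0.0016 for 5. Both are below 0.01. The margin above 0.01 is thin: type I error stays within 0.05 only up to a null rate of 1 − 0.95^(1/5) = 0.0102. This scaling covers true change, not misreading of a subtle one.

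**4. A participant stopped because all rims resolved, with no other event.** Read literally, this participant is replaced.
- Completers: 0/5, p = 1.
- Intent-to-treat: 1/6, p = 1 − 0.99^6 = 0.0585.
- Not replaced and counted: 1/5, p = 0.049.

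**5. If early responders are kept but stopped non-responders are replaced.** Assume that null events occur before any stop and that 10% or 20% of non-responders are replaced.
- 10%: completer null rate = 0.01/(0.01 + 0.99 × 0.90) = 0.0111; type I error = 1 − 0.9889^5 = 0.054.
- 20%: completer null rate = 0.01/(0.01 + 0.99 × 0.80) = 0.0125; type I error = 1 − 0.9875^5 = 0.061.

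**6. Power with 5 participants at lower event rates.** At 0.20: 1 − 0.8^5 = 0.67. At 0.10: 1 − 0.9^5 = 0.41.

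**The case against.** This is a small open-label pilot, its results will also be reported descriptively, and the rims are read blinded to time point. Section 10 is broadly coherent by itself: its null, power and rejection rule all concern change, and Section 1 foresees elimination or perhaps reduction of the rim. On that view the Précis and Section 9 are merely loosely worded.

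Much of this stands. Section 10 can serve as the governing text if the sponsor says so. But the plan states a null hypothesis, a significance level and a rejection rule, and a test needs a defined event. Blinding protects the reading; it does not say whether a faded rim counts.

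Three other points on this side also stand:
- The secondary outcome, "Proportion of paramagnetic rim lesions in which the rim has diminished or disappeared at any time point", is per lesion and covers any time point. It can coexist with either primary event and is not itself a contradiction.
- The definition "Definition of efficacy endpoint: disappearance of one or all paramagnetic phase rims" is loose, but Section 9 goes on to specify all rims for dose escalation, so that trigger is not left wholly open.
- Completer probably means someone who finishes the study visits. Section 4 sends participants stopped for efficacy to the same follow-up visits, so excluding them may not be intended. The replacement rule as written still catches them.

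**Conclusion.** The primary event is contradictory and no passage settles it. The result depends on it in one case only: at least one rim has diminished and none has disappeared at the end of dosing. With one such participant in five, the p-value is 0.049 or 1. The replacement wording is a secondary gap, giving 0/5 (p = 1) or 1/6 (p = 0.0585) according to a choice of set that the plan does not make.

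A reader might infer more than the documents support:
- **That the event definition always decides the trial.** It does not. If a rim has gone, both definitions reject; if none has changed, neither does.
- **That the power or the null is wrong.** The power reproduces, and 0.01 is compatible with 1/29 scaled to 12 weeks under the stated 2-to-5-year assumption.
- **That a participant stopped for resolution vanishes from the analysis.** That participant remains in the intent-to-treat set.
- **That replacement costs a known amount of power.** The documents give no basis for the share of responders who would stop early.

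**What to change.** Settle the following before the end-of-dosing scans are read.

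1. **One event.** State one participant-level yes/no primary event, at the end of dosing on the time-point-blinded read, identically in the Précis, Section 9 and both parts of Section 10. Either choice works:
   - *Disappearance of at least one baseline rim.* Restate 0.01 and 0.28 as assumptions for this event, and give power as 0.81 at 0.28, 0.67 at 0.20 and 0.41 at 0.10.
   - *Diminished or disappeared.* Define *diminished* and align the Précis and Section 9 to Section 10. The stated null and power are kept.

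   Report the proportion of lesions descriptively.
2. **Replacement.** Exempt participants stopped because the efficacy endpoint was met, and count them as evaluable.
3. **Analysis set.** Name the completer or the intent-to-treat set as primary and report the other as supportive. Apply the one-sided exact test at 0.05 to the actual number in the primary set instead of a fixed one-event rule; one event in 6 does not reject. If completers are primary, disclose that replacing stopped non-responders while keeping early responders can lift type I error slightly above 0.05.
4. **Efficacy endpoint wording.** Reconcile the one-or-all definition in Section 9 with its own escalation sentence and with the two references in Section 4. No clinical rule is proposed here.

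**Cost.** Protocol wording only, with no added participants or scans. Under the disappearance event, a rim that only fades no longer supports the primary claim, and power may be lower than 80%. If the intent-to-treat set is primary and grows to 6, rejection needs two events, and power at 0.28 is 1 − 0.72^6 − 6 × 0.28 × 0.72^5 = 0.54. Counting participants stopped for resolution means that some evaluable participants have less than 12 weeks of dosing, which should be reported.

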## 3. Subjects

### Description of study populations

This protocol will enroll up to 10 individuals with progressive or stable MS, evidence of chronic active lesions in the white matter (by MRI), and no evidence of new lesion formation in the prior 3 months or clinical relapse in the prior 12 months (by analysis of prior off-protocol MRI scans). We aim to achieve 5 study completers. NIH employees, regardless of their status as subordinates, relatives, or coworkers of investigators, are eligible.

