## Inclusion criteria

### ***Inclusion criteria:***

- Age  $\geq 18$
- Ability to give informed consent
- If fertile, agreement to use an effective method of birth control during the study and for up to 3 months after the last dose of the study drug
- Agreement not to participate in any other interventional study while participating in this protocol
- Diagnosis of MS, either stable or clinically progressive
- Prior 7-tesla MRI scan, with high image quality in the judgment of the study neuroradiologist, demonstrating at least one white matter lesion with a paramagnetic rim (41)

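### Analysis of variance is unsuitable for the 0/1 rim outcome, and the unit of analysis for T1 and lesion volume is left open

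*Combined protocol and SAP*

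**What the plan says.** Under Analysis of data/study outcomes, section 10 states: "Longitudinal changes in rim presence/absence, T1 relaxation time, and lesion volume will be analyzed by analysis of variance or mixed-effects models". A parenthesis and the next clause continue "which naturally handle missing data), the latter two in comparison to" non-rim lesions. Mixed models are therefore an equal alternative to ANOVA, supported only by how they treat missing data, and the contrast with non-rim lesions applies to T1 and volume but not to the rim outcome. The sentence before says "MRI outcomes will be reduced to scalar measures at various time points", without saying whether that means one value per lesion or one per participant.

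The Secondary outcome measures in section 9 count lesions: "Proportion of paramagnetic rim lesions in which the rim has diminished or disappeared at any time point" and "Changes in size of paramagnetic rim lesions at all time points, relative to non-rim lesions". Entry requires a prior 7T scan "demonstrating at least one white matter lesion with a paramagnetic rim", and the efficacy endpoint in section 9 refers to whether "all paramagnetic rims that were present at baseline are no longer seen". On sample size, section 3 says "We aim to achieve 5 study completers", with up to 10 enrolled.

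No link function, random effect, clustering term or small-sample correction is given. The primary outcome has its own exact binomial test, with a participant-level rejection rule in the Power analysis.

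**The concern.** Two features of the data fit badly with the permitted method.

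First, rim presence is a 0/1 variable that equals 1 for every followed lesion at baseline. ANOVA pools a residual variance across visits, one of which has none by design. The protocol also expects almost no change off therapy, so a trial with no rim loss is plausible.

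Second, lesions are nested in about five people. If T1 and volume are analysed with one row per lesion, the standard error reflects the number of lesions more than the number of people.

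At stake are the intervals and p-values for secondary MRI outcomes. The study has no control arm, and rim versus non-rim is the concurrent comparison named in the analysis section, so readers may lean on it.

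**Working it through.** **The plan's own figure.** Section 10 gives 80% power for n = 5, null 0.01, difference 0.27 (alternative 0.28), rejecting if at least 1 of 5 participants changes. Alpha = 1 − 0.99^5 = 0.0490. Power = 1 − 0.72^5 = 0.8065. The figure reproduces. It belongs to the primary test and does not depend on the ANOVA sentence.

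**Inputs.** From the documents: 5 completers, all followed rims present at baseline, scans at baseline and weeks 4, 8 and 12. Assumed, because the documents do not give them: lesions per participant, ICC and lesion-level loss rate (0.10 or 0.28). Simulations used 20,000 trials per setting.

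**Rim presence, by hand.** If no rim is lost, every value is 1, residual variance is 0, F is 0/0 and the interval for change collapses to the point 0. It then misses any true loss. With one rim lesion per participant, no loss occurs with probability 0.90^5 = 0.590 at loss 0.10 and 0.72^5 = 0.193 at loss 0.28. Coverage cannot exceed 0.410 and 0.807 respectively. Lesion clustering plays no part in this.

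**Rim presence, simulated.** Participant loss rates came from a beta distribution with parameters p(1/ICC − 1) and (1 − p)(1/ICC − 1). Lost rims stayed lost. Coverage (%) of nominal 95% intervals for change from baseline to week 12, at ICC 0.3:

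| Rim lesions each | Loss rate | One-way ANOVA, lesion rows | Repeated-measures ANOVA, participant proportions | t interval, 5 participant changes | Exact interval, any rim lost | Trials with no loss (%) |
|---|---|---|---|---|---|---|
| 1 | 0.10 | 40.6 | 40.0 | 40.8 | 99.1 | 59.1 |
| 1 | 0.28 | 79.6 | 78.2 | 80.3 | 97.7 | 19.5 |
| 2 | 0.10 | 57.4 | 56.9 | 58.1 | 99.7 | 41.9 |
| 2 | 0.28 | 86.4 | 74.7 | 92.3 | 98.7 | 6.4 |
| 4 | 0.10 | 72.2 | 73.0 | 74.7 | 98.6 | 25.2 |
| 4 | 0.28 | 81.4 | 79.6 | 88.1 | 98.4 | 1.6 |
| 8 | 0.10 | 63.8 | 68.3 | 72.3 | 99.7 | 13.9 |
| 8 | 0.28 | 72.1 | 77.7 | 91.2 | 99.7 | 0.3 |

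The exact column targets a different quantity, the probability that a participant loses any rim. At 8 lesions and loss 0.28, the true SD of the change is 0.124 against an average lesion-row standard error of 0.073, a ratio of 1.7. Not every setting fails: at ICC 0 and loss 0.28, lesion-row ANOVA covers 93% (4 lesions) and 94% (8 lesions).

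**T1 and volume.** Change = participant effect (variance ICC) + lesion residual (variance 1 − ICC), with no true difference between lesion types. The test is a lesion-row two-group ANOVA at 5%. False-positive rate (%) at ICC 0.1 / 0.3 / 0.5:

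| Participant effect | 1 rim + 20 non-rim each | 5 rim + 20 non-rim each |
|---|---|---|
| On rim lesions only | 6.0 / 9.6 / 15.3 | 10.0 / 21.7 / 34.5 |
| Separate for each type | 6.3 / 9.7 / 12.9 | 13.5 / 28.1 / 37.7 |
| Shared by both types | 4.2 / 2.7 / 1.3 | 3.9 / 2.5 / 1.4 |

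A one-sample t test on the five participant-level rim-minus-non-rim differences gave 4.8% to 5.2% in all these settings.

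**Exact intervals (95%).** 0 of 5: 0 to 1 − 0.025^(1/5) = 0.522. 1 of 5: 1 − 0.975^(1/5) = 0.005, to 0.716. 2 of 5: 0.053 to 0.853.

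**The case against.** The plan never says that lesion rows are the unit. Reducing MRI data to scalars could mean one value per participant, and repeated-measures ANOVA blocked on participant is a natural reading of a longitudinal analysis. Mixed models are equally permitted, and a suitable one would handle clustering in T1 and volume. A reader might infer that the plan treats lesions as independent and so is bound to give wrong error bars. The text does not support that for T1 and volume: neither the unit nor the model is fixed, and even on lesion rows the error can go either way.

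A reader might also conclude that ANOVA should be struck out altogether. That goes too far. A paired t test on participant-level rim and non-rim means is itself a two-level within-participant ANOVA, with F = t². The fault lies in lesion-row ANOVA, and in any ANOVA of the 0/1 outcome.

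Nor do the documents rank T1 and volume as the main supporting evidence; section 9 lists them among several secondary outcomes. These points stand.

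The participant-level reading does not rescue the rim outcome, since the fourth column above already uses one value per participant and visit. Choosing a mixed model is not enough either. A linear model with only a participant intercept, approximated by participant-block ANOVA on lesion rows, covered 69% at 8 lesions, loss 0.28 and ICC 0.3. A logistic model (which the plan does not name) with a separate baseline level has no finite baseline estimate, because every value there is 1.

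**Conclusion.** For rim presence/absence, the plan permits a method that does not suit the data. This follows from the design: zero baseline variance, and an undefined F when no rim is lost. The size, about 40% to 80% coverage for repeated-measures ANOVA on participant proportions at ICC 0.3, rests on the assumed lesion counts, ICC and loss rates.

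For T1 and volume, the finding is an unspecified unit. If lesion rows were used, the rim versus non-rim test could be too liberal or too conservative. Neither direction nor size can be settled from the documents. With one rim lesion per participant, the entry minimum, the simulated rates run only from about 1% to 15%.

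A reader might infer that the primary result is at risk. It is not: the exact binomial test, its rejection rule and the stated power do not use this sentence. The change should be made before analysis, but the issue is confined to secondary outcomes.

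**What to change.** **Rim presence.** Replace ANOVA with the number of participants who have lost any baseline rim, at each post-baseline visit, with the number assessed and an exact binomial 95% interval. Leave baseline out of the inference. A t interval on participant proportions is not an adequate substitute, as the table shows. Keep the lesion-level proportion as description.

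**T1 and volume.** State that the participant is the unit of inference, and rule out ANOVA on lesion rows. Choose one method in advance: either a paired contrast of each participant's mean rim change minus mean non-rim change, or a mixed model with participant, participant-by-lesion-type and lesion effects and small-sample degrees of freedom. With five participants the variance components will be poorly estimated, so the paired contrast (4 degrees of freedom) is the simpler choice.

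**Cost.** A few lines in section 10 and no new data. Intervals will often be wider, and the any-rim-lost count ignores how many rims a participant lost. Sample size and the primary analysis stay as they are.

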## 4. Study Design and Methods

### Study overview

Screening will be done under an existing Neuroimmunology Clinic protocol that allows collection of data required for determining eligibility. Prospective participants who meet eligibility requirements will then provide informed consent and undergo baseline procedures. Following training on self-administration of subcutaneous injections, subjects will be started on initial dose of study drug of 100 mg/d. Participants will have a scheduled follow-up phone call at 24–48 hours following the first dose to assess for any adverse reactions or concerns. Subsequent routine assessment of tolerability and safety will be made at the time of scheduled study visits. For the duration of the study, including dose escalation and follow-up phases, participants will undergo assessments at NIH. Telehealth may be used for conducting routine visits to the NIH Clinical Center. Participants will return at weeks 4 and 8, at which time they will undergo clinic visit, lab work, and 7T brain MRI. As long as no treatment-limiting toxicity is encountered (see “safety endpoints,” Section 8.4) AND the study endpoint is not met (see “efficacy study endpoint,” primary outcome, section 9), the dose will be escalated every 4 weeks to a target dose of 300 mg/day, which will be administered for a further 4 weeks. The final on-treatment study visit will be at week 12. At that time, the drug will be discontinued, with off-treatment visits at weeks 16 and 24 (4 and 12 weeks following treatment discontinuation). The study timeline is in **Error! Reference source not found..**

## Fig. 2

- **MRI at week 24 will be done without Gadolinium, unless clinically indicated.**

Should early drug discontinuation occur, either due to dose-limiting toxicity or to achievement of efficacy endpoint, off-treatment follow-up visits will proceed 4 and 12 weeks after treatment interruption. If a 7T scan cannot be obtained within window at any particular study visit, a 3T MRI can substitute. Leftover biological samples will be stored for future analysis.

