- **Weeks 4, 8, and 12.** At each visit, sharps boxes and empty vials will be collected. Participants will undergo a brief clinical interview/exam, lab work (to include clinical laboratory studies required for safety monitoring such as CBC with differential and blood collection for research purposes as detailed in Section 9, Exploratory Outcome Measures), clinical scales and LP (week 12 only), and 7T MRI (with gadolinium, if not contraindicated). We may collect up to 175 mL of blood at the week 4, week 8, and week 12 visit not to exceed the Clinical Center's policy for limits of blood drawn for research purposes. The window for these visits will be  $\pm 7$  days.
- **Week 16 (or 4 weeks after dosing discontinuation).** Participants will undergo a brief clinical interview, lab work (clinical and research), 7T MRI (with gadolinium, if not contraindicated). We may collect up to 155 ml of blood at the week 16 visit. The window for this visit will be  $\pm 7$  days.
- **Week 24 (or 12 weeks after dosing discontinuation).** Participants will undergo a brief clinical interview, lab work (clinical and research), clinical scales, LP, and 7T MRI (without gadolinium, unless clinically indicated). We may collect up to 175 mL of blood at the week 24 visit. The window for this visit will be  $\pm 7$  days.

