## Criteria for Early Discontinuation of Dose Escalation

Dose escalation will be discontinued in the following situations:

- Dose Limiting Toxicity is observed, as defined in Section 8.
- Efficacy Study Endpoint is achieved, as defined in Section 9.

CNS IRB Protocol Template (5.4.17)

- The patient is found to be pregnant.
- The patient, for any reason, is unwilling to continue treatment with study drug.

In the event of early discontinuation of dose escalation, the patient will proceed directly to the off-treatment follow-up phase of this study.

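### Participants who lose all rims leave the on-drug visits by rule, and the stated reliance on mixed models does not by itself protect the T1 and lesion-volume time courses

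*Combined protocol and SAP*

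**What the plan says.** **Method.** Section 10 (Analysis of data/study outcomes) states that longitudinal rim status, T1 and "lesion volume will be analyzed by analysis of variance or mixed-effects models (which naturally handle missing data"), with T1 and volume compared with non-rim lesions. Analyses are planned in completers and by intent-to-treat. The section does not give a time scale, a missing-data assumption or a definition of a completer.

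**Outcomes.** Section 9 (Secondary outcome measures) lists "Changes in T1 relaxation time within paramagnetic rim lesions at all time points, relative to non-rim lesions", and the same for lesion size.

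**Exit rule.** Section 9 (Primary outcome measures) sets the rule for each visit during dosing: if "all paramagnetic rims that were present at baseline are no longer seen, dose escalation will end and the subject will proceed into the post-treatment follow-up". Section 4 (Criteria for Early Discontinuation of Dose Escalation) agrees: "In the event of early discontinuation of dose escalation, the patient will proceed directly to the off-treatment follow-up phase of this study".

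**Scans after exit.** Section 4 (Study overview) says that after an early stop "off-treatment follow-up visits will proceed 4 and 12 weeks after treatment interruption". Specific procedures labels the first of these "Week 16 (or 4 weeks after dosing discontinuation").

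**Replacement.** Section 10 (Power analysis) replaces participants in whom anakinra is stopped and makes no exception for efficacy stops.

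**The concern.** A likelihood-based mixed model gives valid estimates with incomplete data when missingness depends only on observed values that the model contains. Here the reason for leaving the on-drug visits is rim status. The T1 and volume models are described only as comparisons of rim with non-rim lesions over time, without current rim status. Earlier T1 or volume values carry some of the information about exit, but not all of it.

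The alternatives that the plan allows are weaker. Repeated-measures analysis of variance in its usual complete-case form drops anyone without every visit. The completer analysis may do the same, because completer is undefined and the replacement rule treats an efficacy stop like any other stop.

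If T1 or volume improves most where rims disappear, the week-8 and week-12 on-drug means lose the participants with the largest changes. They would then be read at the 200 and 300 mg/day steps as weaker effects than the drug produced.

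**Working it through.** **1. The plan's own figure.** Inputs from Section 10 (Power analysis): n = 5, null proportion 0.01, difference 0.27, reject if at least 1 participant changes.
- One-sided alpha = 1 − 0.99^5 = 0.049.
- Power at 0.01 + 0.27 = 0.28 is 1 − 0.72^5 = 0.807.

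The stated 80% reproduces. It concerns the primary test. It is used here only because 0.28 is the plan's one response rate. That rate counts any lesion change, so it is an upper bound for loss of all rims.

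**2. Who is scanned when** (Section 4):

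| Stop | On-drug scans after baseline | Off-drug scans, actual week |
|---|---|---|
| Week 4, all rims gone | 4 | 8, 16 |
| Week 8, all rims gone | 4, 8 | 12, 20 |
| Week 12, full course | 4, 8, 12 | 16, 24 |

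The scan that triggers a stop is itself on drug. Week 8 therefore selects on rims at week 4, and week 12 selects on rims at week 8.

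**3. How often.** Assumption: a share q loses all rims by week 12, one third at each of weeks 4, 8 and 12. The chance that a given participant stops before week 12 is 2q/3, so P(at least one of 5) = 1 − (1 − 2q/3)^5.
- q = 0.01: 0.03
- q = 0.10: 0.29
- q = 0.28: 1 − 0.8133^5 = 0.64, with 5 × 0.187 = 0.93 stops expected
- q = 0.50: 0.87

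**4. Available on-drug cases at week 12, q = 0.28.** Further assumption: T1 or volume changes only in those who clear. Their share among participants still on drug is (q/3)/(1 − 2q/3) = 0.0933/0.8133 = 0.115, against 0.28 in the whole cohort. Shortfall = 1 − 0.115/0.28 = 59%.

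**5. Mixed model on on-drug scans only, q = 0.28.** Large-sample simulation with three on-drug visits, unit variance, a responder effect growing linearly to 1 SD at week 12, and an unstructured normal model for T1 alone. At within-person correlation 0.5 the true week-12 mean change is −0.28 SD and the model gives −0.16 SD, a shortfall of about 42%. Over correlations 0.3 to 0.8 the shortfall runs from about 48% down to 36%. The absolute bias at 0.5 is 0.12 SD, against a standard error of 1/√5 = 0.45 SD for a mean of 5.

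**6. Rim status for comparison, q = 0.28.** Raw on-drug rim loss is 0.093 at week 4, 0.0933/0.9067 = 0.103 at week 8 and 0.115 at week 12. Multiplying the interval-specific probabilities of keeping rims gives cumulative losses of 18.7% at week 8 and 28% at week 12, which are the true values. The rim series is recoverable from its own history.

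**7. Sensitivity of the T1 and volume shortfall.**
- Non-responders have half the effect: available cases give 0.5 + 0.5 × 0.115 = 0.557 against 0.5 + 0.5 × 0.28 = 0.64, a 13% shortfall.
- Only a quarter of the 28% clear all rims and stop early, and the rest stay on drug: 12–16% (mixed model) and about 20% (available cases).
- Nobody clears before week 12: nil.

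**The case against.** The strongest reply is that efficacy stoppers are not lost. They are scanned 4 and 12 weeks after stopping, the secondary outcomes cover all time points, and an intent-to-treat analysis is planned. If the post-stop scans enter at their actual week, and the effect is assumed to hold at its stopping level, a T1-only model comes within about 11% of the intent-to-treat week-12 mean, even if all responders stop by week 8. This stands, but Section 10 does not say that those scans are used that way. The intent-to-treat mean also mixes on-drug and off-drug scans, and a week-4 stopper still has no scan at actual week 12.

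Also correct: a mixed model uses stoppers' earlier scans, and the bias is small beside the sampling error of five participants.

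A reader might infer that the week-8 and week-12 estimates come only from people who kept their rims. They do not, because participants who clear at the visit itself are included.

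A reader might also infer from the week-16 label that scans at different actual weeks are pooled in one cell. That label belongs to a visit schedule; Section 10 names no time scale, so the pooling is possible but not stated.

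**Conclusion.** The point holds for T1 and lesion volume as a minor one. Exit depends on rim status, the models as described omit it, and the parenthesis about missing data does not settle the matter. With 0.28 as an upper bound and losses spread evenly over weeks 4, 8 and 12, there is about a 64% chance of at least one early efficacy stop. The on-drug week-12 mean is then understated by about 36–48% (mixed model on on-drug scans) or about 60% (available cases). These figures rest on an assumed rate of all-rim loss and an effect confined to those who clear. They shrink if few responders clear all rims or if non-responders also change.

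Three stronger readings are not supported:
- **Rim presence and the primary outcome are biased in the same way.** Rim exit depends on observed rim history, and the primary outcome is read at the end of each participant's dosing.
- **The shortfall is 64–100%.** That needs every responder to lose all rims by week 8. So does an 81% chance of a stop (1 − 0.72^5).
- **The trial's conclusion is at risk.** The rejection rule does not use these models.

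The direction stated here concerns the rim-based exit only. Section 8 also stops drug for obvious lesion enlargement, which acts on the volume outcome separately.

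**What to change.** Change the wording of Section 10; no new scans or participants are needed.

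1. Delete the analysis-of-variance option and the parenthesis on missing data. State the missing-data assumption instead.
2. Define the on-treatment contrast for T1 and volume as baseline to each participant's last on-drug scan. This matches the primary outcome's end-of-dosing time point. Report exposure beside it.
3. Fit the longitudinal mixed model on actual weeks since first dose, with on/off-drug status or weeks since last dose, and keep the post-stop scans.
4. Count efficacy stops as completers in the completer analysis.
5. Report the number absent from each on-drug visit, with reasons, and show individual trajectories.
6. State that week-8 and week-12 on-drug means will not be read as dose-specific effects.

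Rim status at the previous scan should not be added as a covariate. It is a response to treatment, and its all-rims-gone level never occurs on drug.

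The exit trigger determines who leaves, so the efficacy definition in Section 9, "Definition of efficacy endpoint: disappearance of one or all paramagnetic phase rims", must be reconciled with the all-rims rule beside it.

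The cost is that the end-of-dosing contrast pools 4 to 12 weeks of exposure and is not a 12-week effect.
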